4.4. Sample Size

An overall population size of 44 asthmatic subjects was based on the following assumptions:

- Type I error probability $\alpha = 5\%$
- Effect size = $(\mu_1 - \mu_0) / \sigma$
 - μ_i = mean PEP in group i ($i=1$: OC459, $i=0$: placebo),
 - σ = standard deviation of PEP
- PEP is primary end-point (=total daily lower respiratory symptom scores over D0 to D14, potential maximum of 315).

Based on a previously completed trial with similar design conducted at the same study site [10], σ is estimated to be 21.15 and the effect size equal to 22.21, yielding $n=15$ evaluable subjects per treatment group at 80% power. This is grossed-up for 80% rhinovirus inoculation success and adjusted for expected drop-outs to yield 22 enrolled patients per treatment group.

4.5. Treatment Groups

- OC459: 50mg to be taken orally as one tablet, once daily, for 5 weeks in total.
- Placebo: to be taken orally as one tablet, once daily, for 5 weeks in total.

4.6. Randomisation

Subjects who meet the relevant criteria and provide informed consent will be randomised to either OC459 or placebo in a 1:1 ratio. Randomisation will occur at a baseline visit after the screening visit(s), and will be in blocks of four in order to balance the number of patients allocated to each treatment group. A dummy unblinded randomisation list (taking into account the blocking requirements) will be generated by the trial statistician and tested. Once tested, a statistician working independent to the trial will create the final list for entering into the study database. This file will be password protected, with unblinding instructions provided by the database development team to the investigators.

At randomisation, the database will be interrogated and each new subject assigned the next sequential randomisation item on the list. The unblinded randomisation list will also be provided to the manufacturer, Atopix Ltd, in order to label IMP/placebo appropriately prior to dispensing to pharmacy. Thus the investigators, pharmacy and subjects will all be blinded.

4.7. Withdrawal and Replacement

Subjects who are considered evaluable (confirmed rhinovirus infection) and have completed at least 14 days post inoculation with RV-16 will be included in the analysis. Subjects lost to follow up will not be replaced if they were evaluable with sufficient data to assess the primary outcome. Subjects who are either withdrawn from the trial or who chose to discontinue participation and do not meet these criteria will be replaced until a sufficient number of evaluable subjects are reached (n=30).

4.8. Unblinding

Ceasing treatment rather than unblinding will be encouraged as far as possible. However, where knowledge of the treatment will assist in management of acute illness / emergency treatment, unblinding will be supported. The decision to unblind will be made by the Chief Investigator, with the Trial Steering Committee convened ad hoc if necessary to support the decision. Study participants will be provided with a Patient Alert Card indicating the study number and a 24 hour emergency contact number.

Unblinding will take place in line with the standard operating procedure used with the database. Specifically, once the decision has been made to unblind a subject, one of the study team will access the database and enter the subject details and study drug code. As soon as this is entered into the system, an email will be sent to the Trial e-mail address, the trial statistician, the Chief Investigator and the database team warning of a potential unblinding. The essential subject information will be checked against the data in the database and queries raised if they do not agree. The unblinding will not be actioned if there is a discrepancy between the data stored and the data entered. Once this information is accurately completed, a second form must be filled in to confirm the unblinding. The unblinded information will then be displayed, and a second email sent to the Trial e-mail address, the trial statistician, the Chief Investigator and the database team confirming the subject has been unblinded. This email will not continue details of the unblinded treatment. If the site unblinding account has been used, the database support team will set a new, pre-expired password and send new unblinding instructions to the study team.

[figure not shown]
The Chief Investigator will review the cause and results of the unblinding process with the study team, and possibly the Trial statistician, and document/implement any follow-up actions.

4.9. Schedule of Time and Events

Table 1: Schedule of Visits and Events

	Screening visit 1	Screening visit 2	Visit 1 (baseline)	Visit 2	Visit 3	Visit 4	Visit 5	Visit 6	Visit 7	Visit 8	Visit 9	Visit 10	Visit 11
Study day			-21	-9	-8	0	2	3	4	5	7	10	42
Ideal weekday			F	W	T	F	Su	M	T	W	F	M	F
Visit length	30 min	60 min	60 min	45 min	3 hr	60 min	45 min	45 min	45 min	3 hr	60 min	45 min	30 min
Skin prick test	X												
Viral serology	X												X
Asthma Control Questionnaire (ACQ)	X		X	X		X						X	X
Spirometry (in clinic)	X		X	X		X	X	X	X	X	X	X	X
Histamine challenge (PC ₂₀)		X	X	X							X		
Exhaled nitric oxide (FeNO)		X	X	X		X		X		X	X	X	X
Blood tests		X	X		X			X		X		X	X
ECG		X											
Urine pregnancy test		X											
Chest radiograph		X											
IMP or placebo administration			Daily from day -21 → day 14 (then stop)										
Nasosorption			X			X	X	X	X	X	X	X	X
Nasal lavage			X			X	X	X	X	X	X	X	
Nasal scrape			X		X			X		X			
Bronchoscopy (bronchosorption, BAL, brushings, biopsies)					X					X			
Sputum induction			X	X					X		X		
Virus inoculation						X							
Symptom diaries including spirometry and medication			Daily at home during study period →										
Spirometry (portable, at home)			Daily at home during study period →										

Table 2: Schedule of Treatment and Events

4.10. Study Baseline

For Primary and Secondary endpoint assessments, baseline will be determined as the last measurement taken prior to virus inoculation i.e. Day 0 (ACQ-6, home PEFR, home FEV1, clinic FEV1, clinic FVC, FeNO, virus load, soluble mediators) where available. If/where this is missing, the value on the previous visit will be used, for example, laboratory bloods and PC20 (for laboratory bloods, the sample on day -8 will be taken as a baseline, for PC20, the result from day -9 will be taken).

Demographic baseline variables will be taken at Screening, Day -21 and Day 0 (where available).

5. Analysis Sets

5.1. Safety analysis set

The safety analysis set includes all subjects who were randomized and received at least one dose of study medication.

5.2. Full analysis set

The full analysis set (FAS) includes subjects who:

- Are randomised into the study (D-21)
- Have been inoculated with the rhinovirus serotype 16 (RV-16) challenge virus (D0)
- Have confirmed RV-16 infection, defined as either (i) positive RV-16 PCR in nasal lavage at any time after inoculation (D0) or (ii) seroconversion (positive antibodies to RV-16 at a titre of at least 1:4 at the final study visit)
- Have completed at least 14 days post inoculation with RV-16.

These subjects are defined as 'evaluable' and form the basis of the power calculation.

The FAS will be used to assess the primary objective and will be used to analyse all efficacy endpoints plus any post-infection mechanistic outcomes.

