9.15 SPUTUM INDUCTION

Sputum induction will be performed on study visits as per Table 1, in accordance with ERS guidelines[27].

- Subjects will be pre-medicated with 200µg salbutamol via metered dose inhaler and large volume spacer and baseline FEV₁ measured after 10 minutes.
- If the subject's FEV₁ is ≥60% of predicted, the following procedure should be used:
 - Administer 3-4.5% hypertonic saline via nebulizer.
 - Perform 2-5 minutes of inhalation then stop inhalation and check FEV₁ reading.
 - Repeat this process 3 times (i.e. a maximum of 20 minutes).
- If the subjects FEV₁ <60% of predicted, the following should be used:
 - Use normal saline (0.9%) initially.
 - Perform 30 seconds of inhalation then stop inhalation and check FEV₁ reading.
 - Repeat this process for 1 min and then 2 mins of inhalation.
 - Repeat this process with 3% saline with inhalations of 30 secs, 1 min and 2 mins.
 - Repeat this process with 3-4.5% hypertonic saline for 30 secs, 1, 2, 4, and 8 mins.
- In either case if the subject's FEV₁ drops by 20% at any time, or if the subject experiences excessive coughing, bronchoconstriction, hyperventilation, dyspnoea, dizziness, nausea and vomiting, or an increased wheeze, the induction should be stopped immediately and rescue therapy given.

Sputum plugs are selected from saliva by macroscopic inspection of the sample. An aliquot is analysed, unprocessed, for virus load by quantitative PCR. The remaining sample is processed

and centrifuged to separate the cells, which are then stained and counted for differential cell counts.

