10.2 DATA ANALYSIS

Subjects completing the study protocol will be defined as infected or un-infected (neutralising antibody to RV-16 at 6 weeks post inoculation at a titre $<1:4$ and no detection of RV-16 by qPCR in nasal lavage, sputum or BAL at any point after inoculation). Only subjects with confirmed rhinovirus infection will be included in statistical analysis.

Quantitative assessments of symptom scores, lung function, exhaled nitric oxide (FeNO), airway hyperresponsiveness (histamine challenge, PC_{20}), virus load, inflammatory cell numbers and inflammatory markers will be compared within subjects to determine differences between baseline and during infection. Within-subject differences will be analyzed using ANOVA and 2-tailed paired Student's t-tests or Wilcoxon signed rank test as appropriate.

Differences between the patients taking OC459 and placebo group will be analyzed using unpaired parametric or non-parametric analysis as appropriate at each phase of the study. Correlations between (but not limited to) the following will be examined using Spearman's rank correlations to investigate possible causal relationships:

- illness severity (symptoms, lung function, airway hyperresponsiveness)
- virus load
- inflammatory cell counts
- inflammatory markers
- gene expression

Data and all appropriate documentation will be stored for a minimum of 10 years after the completion of the study, including the follow-up period.

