3.1. Primary Endpoint Variable

- Total Lower Respiratory Tract Symptoms Score after rhinovirus infection (sum of daily scores day 0 to day 14)

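### The SAP drops sputum and BAL PCR from the protocol's infection definition, so a subject positive only in the lower airway and without a qualifying Day 42 titre is infected under the protocol but outside the primary analysis set

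*SAP*

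**What the plan says.** **Protocol 10.2 (Data Analysis)** defines the un-infected subject by two conditions that must both hold: a neutralising titre below 1:4 six weeks after inoculation, and "no detection of RV-16 by qPCR in nasal lavage, sputum or BAL at any point after inoculation". It adds: "Only subjects with confirmed rhinovirus infection will be included in statistical analysis".

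**SAP 5.2 (Full analysis set)** accepts infection as confirmed by either of two routes. Criterion (i), the PCR route, reads "positive RV-16 PCR in nasal lavage at any time after inoculation (D0". Sputum and BAL are not named. Criterion (ii), the alternative, is serological: an RV-16 antibody titre of 1:4 or higher on Day 42, which the SAP labels seroconversion. The FAS also requires randomisation, inoculation and at least 14 days of follow-up after inoculation. Its members are the evaluable subjects, and "The FAS will be used to assess the primary objective and will be used to analyse all efficacy endpoints".

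**The primary endpoint** (SAP 3.1) is the "Total Lower Respiratory Tract Symptoms Score after rhinovirus infection (sum of daily scores day 0 to day 14".

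**Sampling** (Table 1 in both documents): after inoculation, nasal lavage is taken on Days 2, 3, 4, 5, 7 and 10, sputum on Days 4 and 7, BAL on Day 5, and RV-16 serology on Day 42 only. For sputum, Protocol 9.15 states: "An aliquot is analysed, unprocessed, for virus load by quantitative PCR". The BAL procedure (Protocol 9.14.3) lists cell mRNA, flow cytometry, proteins and cytokines, but no viral qPCR.

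**The concern.** Infection status is settled after randomisation and decides who enters the primary analysis. The two documents settle it by different rules, and the narrower one governs the FAS. The SAP does not say why it differs, although in 4.3 it openly notes another matter that the protocol's eligibility list lacks, so an oversight is plausible.

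With about 15 evaluable subjects per arm, one reclassified subject is a visible share of the data. The drug is also being tested for effects on viral load and antiviral response, so membership of the set is not obviously independent of treatment. If the difference is noticed only after unblinding, someone must choose a rule with the allocation in view. It is also awkward for a lower respiratory endpoint to leave out a subject whose virus was shown in the lower respiratory tract.

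**Working it through.** **1. The plan's own figure.** Inputs from SAP 4.4 and 7.2: two-sided alpha 5%, power 80%, SD 21.15, and 22.21 for the effect. The plan's n is reproduced only if 22.21 is read as a raw mean difference.

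n per arm = 2 × (1.960 + 0.842)² × (21.15 / 22.21)² = 14.24, rounded up to 15.

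This matches the stated 15 per arm (30 evaluable). Power at 15 per arm is 82.0% by the normal approximation and 79.3% by the t distribution. The infection definition does not enter this calculation, so the figure stands.

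**2. The two rules.** The protocol's un-infected condition is (titre below 1:4) AND (nasal, sputum and BAL all negative). Its negation gives:

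- Protocol, infected: nasal positive OR sputum positive OR BAL positive OR titre at least 1:4.
- SAP, infected: nasal positive OR titre at least 1:4.

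| Nasal PCR | Sputum or BAL PCR | Day 42 titre | Protocol 10.2 | SAP 5.2 |
|---|---|---|---|---|
| Positive | any | any | infected | infected |
| Negative | positive | at least 1:4 | infected | infected |
| Negative | positive | below 1:4 | infected | **not infected** |
| Negative | positive | missing | infected | **not infected** |
| Negative | negative | at least 1:4 | infected | infected |
| Negative | negative | below 1:4 | un-infected | not infected |

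The rules part only in the two marked rows.

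**3. Can Day 42 serology be missing in an otherwise evaluable subject?** Yes. The FAS needs only 14 days after inoculation, and Protocol 9.17 does not replace a subject lost to follow-up who has confirmed infection and a complete diary to Day 14. Such a subject has no antibody route, so PCR is the only way into the FAS. Protocol 10.2 speaks of subjects who complete the protocol, but 4.4 and 9.17 plainly intend early leavers with confirmed infection to count.

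**4. What is disregarded.** Up to three post-inoculation samples per subject: sputum on Days 4 and 7, and BAL on Day 5 if viral qPCR is run on it.

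**5. Size, as an assumed range.** The documents give no rate of lower-airway-only detection. Each subject affected is 1/30 = 3.3% of the evaluable total. If k subjects were lost and *not replaced*, power at a standardised effect of 22.21/21.15 = 1.05 with (30 − k)/2 per arm would be:

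| k lost (assumed) | Evaluable | Normal approximation | t-based |
|---|---|---|---|
| 0 | 30 | 82.0% | 79.3% |
| 1 | 29 | 80.7% | 77.8% |
| 2 | 28 | 79.3% | 76.3% |
| 3 | 27 | 77.9% | 74.6% |

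These figures are illustrative: k is assumed, the primary test is Mann-Whitney rather than a t-test, and SAP 4.7 provides for replacement.

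**The case against.** **The antibody route rescues many of these subjects.** A reader might infer that infections seen only in the lower airway are dropped as a class. They are not. Criterion (ii) is an alternative in the same sentence and keeps any such subject with a Day 42 titre of at least 1:4. Although labelled seroconversion, it sets no condition on the screening titre, which narrows the affected group further. This objection stands and limits the point to the two marked rows.

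**The group needs a run of coincidences.** Inoculation is intranasal, up to six nasal lavages must all be negative, and serology must fail to qualify the subject. This also stands; the group may be empty.

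**The evaluable number is protected.** A reader might infer that the site counts evaluability by the protocol's rule, stops replacing too early, and leaves the analysis short of 30. The documents do not say so. The protocol's replacement text (4.4 and 9.17) refers to confirmed infection without naming specimens. SAP 4.7 replaces up to 30 evaluable subjects, and SAP 5.2 defines evaluable as the FAS. Within the SAP the count and the set agree, so a shortfall does not follow.

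**Nasal-only ascertainment has merits.** Nasal lavage is scheduled at six post-inoculation visits, against two for sputum and one for BAL, and it is the specimen for the protocol's viral-load outcome. That would be a respectable reason for a nasal-only rule, but the SAP does not give it, and it does not remove the conflict with Protocol 10.2.

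**Conclusion.** The point holds in limited form. The protocol and SAP define confirmed infection differently, and the difference bears on the primary analysis set. It affects only subjects who are PCR-positive in sputum or BAL alone and whose Day 42 titre is below 1:4 or missing.

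The size is unknown: the documents support neither a frequency nor a difference between arms. No stated sample-size figure is wrong because of it. Since SAP 4.7 replaces to 30, the main effect is on who is analysed, and the power losses above apply only if affected subjects are not replaced. The conclusion rests on reading the protocol's infected category as the complement of its un-infected one. For Day 5, it also rests on viral qPCR being run on BAL, which only Protocol 10.2 mentions. It is worth correcting because the rule acts after randomisation in a small trial and is cheap to settle in advance.

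**What to change.** Before unblinding:

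1. Amend SAP 5.2(i) so that RV-16 PCR positivity in nasal lavage, in sputum or, where assayed, in BAL, at any time after inoculation, confirms infection, as Protocol 10.2 implies.
2. Confirm whether viral qPCR is run on BAL and, if so, describe it alongside the BAL procedure.
3. Use this single definition for the evaluable count, replacement and the FAS.
4. List by arm any subject who qualifies on a lower-airway sample only.

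If nasal-only was intended, the SAP should say so and justify the departure from the protocol.

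The cost is about one line of the SAP plus a short listing. Sputum qPCR is already planned; BAL may need an assay that the procedures do not describe. The small downside is that subjects without a sputum or BAL sample have fewer chances to test positive; the listing shows whether that matters.

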4.4 WITHDRAWAL CRITERIA

Participants will be free to discontinue trial medications at any point during the study without giving reason. Where possible, follow up will continue. If a participant chooses to withdraw consent, data up to the point of self-withdrawal will be included unless the participant chooses otherwise.

Investigators will withdraw any subject if they are unable to tolerate the study medications, or if the a research investigator feels this is necessary or appropriate. In all cases, the reason for withdrawal must be recorded on the case report form and in the subject's medical records. Subjects will be closely monitored by the Clinical Research Fellow. This is defined further in the section on 'Serious Adverse Events'.

Subjects who are considered evaluable (i.e. confirmed rhinovirus infection) with sufficient data to assess the primary endpoint (i.e. complete diary cards of symptoms up to day 14 post-rhinovirus infection) will be included in the analysis. Subjects who are either withdrawn from the trial or who chose to discontinue participation and do not meet these criteria will be replaced until a sufficient number of evaluable subjects are reached (n=20).

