9.17 LOSS TO FOLLOW-UP

Participants who are lost to follow up will not be replaced if they were evaluable (i.e. confirmed rhinovirus infection) and there is sufficient data to assess the primary outcome (i.e. complete diary card of symptoms to day 14 post-rhinovirus infection). Subjects who are lost to follow up and do not meet these criteria will be replaced until a sufficient number of evaluable subjects are reached (n=20).

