10 STATISTICS AND DATA ANALYSIS

10.1 SAMPLE SIZE CALCULATION

The sample size determination is based on the following assumptions:

Type I error probability $\alpha = 5\%$

Effect size = $(\mu_1 - \mu_0)/\sigma$, where

μ_i = mean PEP in group i ($i=1$: OC459, $i=0$: placebo),

σ = standard deviation of PEP, and

PEP is primary end-point (=total daily lower respiratory symptom scores over d0 to d14).

Based on a previously completed trial with similar design conducted at the same study site [10], σ is estimated to be 21.15 and the effect size equal to 22.21, yielding $n=15$ evaluable subjects per treatment group at 80% power. This is grossed-up for 80% rhinovirus inoculation success and adjusted for expected drop-outs to yield 22 enrolled patients per treatment group.

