7.2. Primary Analysis

Uncorrected lower respiratory symptom scores collected from D0 to D14 will be aggregated to create an overall total for each patient. Where patient scores are missing, data will be imputed based upon rules set within Section 7.5. Patients missing $\geq 20\%$ of score data will be excluded from any additional per-protocol analyses.

Data will be presented using summary statistics per treatment group and will include median and interquartile range (IQR). A supplementary plot showing individual measurements for both groups with a box & whisker overlay showing median and IQR will be produced.

Primary analysis to test for difference between the mean aggregated scores of the two treatment groups will be carried out using Mann-Whitney U tests. Differences will be considered significant at $P < 0.05$. All P values are two-sided.

An additional secondary analysis will take place correcting the scores for bronchoscopy-related symptoms. Full methodology will be clarified within Section 7.3.1 below.

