7.5. Missing Data and Withdrawn Subjects

Missing values for primary and secondary endpoints (as per Table 03), viral load and soluble mediators will be extrapolated for cumulative / area under the curve calculations.

Imputation will be based upon the values before and after the missing timepoint(s). Missing values will be derived using the following formula:

$$x_n = x_{(n-1)} + z$$

Where:

x_n = missing value at day 'n'

$x_{(n-1)}$ = last recorded value before missing data begins

z is a constant derived from the last recorded value $x_{(n-1)}$, the first value obtained after missing data y , and d = the number of missing data points between $x_{(n-1)}$ & y

$$z = \frac{y - x_{(n-1)}}{d + 1}$$

For example; if we are missing data at day 4 and we know that the value at day 3 is 1 and the value at day 5 is 3 then we can calculate constant z as $z = \frac{(3-1)}{(1+1)} = 1$ thus the missing value at day 4 would be: $x_4 = (x_3 + 1) = (1 + 1) = 2$.

Imputation and analysis involving missing and imputed data will be taken under the assumption that the data is missing-at-random (MAR).

If imputation has taken place, sensitivity analyses will be performed to ensure integrity of statistical testing based on extrapolated scores.

No other values for missing data will be imputed.

If there is a missing baseline value for virus load, the previous value (i.e. at randomisation / day - 21) will be taken (virus load should be below the lower limit of detection prior to inoculation). If there is a missing baseline value on another variable and after unblinding the subject is in the placebo group, the baseline will be replaced with a value from a previous visit (e.g. randomisation / day -21) if available. If after unblinding the subject is in the treatment group, the baseline will not be replaced (with the exception of virus load, as above).

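### The primary total is undefined for a symptom diary that stops before Day 14 and never resumes, and the protocol and SAP disagree on whether that subject is analysed

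*SAP*

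**What the plan says.** **Who is analysed.** Protocol 4.4 includes subjects with confirmed infection and "complete diary cards of symptoms up to day 14 post-rhinovirus infection". Protocol 9.17 applies the same test to loss to follow-up: "complete diary card of symptoms to day 14 post-rhinovirus infection". SAP 5.2 defines the full analysis set (FAS), which carries the primary analysis, by randomisation, inoculation, confirmed infection and one further item: "Have completed at least 14 days post inoculation with RV-16". The diary is not mentioned. SAP 4.7 repeats the 14-day rule for inclusion. Its replacement rule for loss to follow-up asks for enough data for the primary outcome but does not say how much that is.

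**How the total is formed.** The primary endpoint is the sum of daily lower respiratory scores over Day 0 to Day 14, 15 days in all (SAP 6.2). SAP 7.2 creates a total for every patient, sends missing scores to section 7.5, and excludes patients missing 20% or more of scores from per-protocol analyses only.

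**How gaps are filled.** SAP 7.5 interpolates linearly between the last value before a gap and the first value after it, then states: "No other values for missing data will be imputed". Sensitivity analyses follow if imputation took place.

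**What limits the problem.** Protocol 9.4 continues the diary for six weeks after inoculation.

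**The concern.** Two faults meet in the same subjects. First, the documents set different conditions for entering the primary analysis, so a confirmed-infected subject with an incomplete diary is outside the analysis under one and inside it under the other. The visit schedule goes from Day 10 to Day 42, so having completed 14 days does not show that scores were recorded on those days.

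Second, the SAP lets such subjects in but has no rule for one kind of gap. The endpoint is a sum: a day with no value, left out of the addition, lowers the total, and the Mann-Whitney test then ranks that subject as having few symptoms. If the total is instead treated as missing, the subject leaves the primary comparison although still in the FAS. With about 15 subjects per arm, a handful of such diaries, unequally split, can move the comparison. The choice between the two treatments would be made after the data are in.

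**Working it through.** **1. The plan's own figure.** Inputs: alpha 5% (Protocol 10.1), two-sided (SAP 7.2), 80% power, and an SD that "is estimated to be 21.15 and the effect size equal to 22.21" (SAP 4.4). The value 22.21 reproduces the sample size only as a difference in points, which is 22.21/21.15 = 1.05 SD. Normal approximation: n = 2 × (1.96 + 0.842)² × (21.15/22.21)² = 14.2, rounded up to 15 per group, as stated. Power at 15 is 82.0%. The t-test version needs 15.3 and gives 79.3% at 15. So 22.21 points is a fair yardstick.

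**2. The interpolation rule.** The step is z = (y − x)/(d + 1), where x is the last value before the gap, y the first value after it and d the number of missing points.
- Diary missing Days 12 to 14, resumed on Day 15, 4 points a day throughout: z = (4 − 4)/4 = 0, each gap day is 4, and the full 60 is recovered.
- The same diary never resumed: y does not exist, z is undefined, and no other rule applies.

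**3. What a partial sum keeps, assuming a flat score.**

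| Last entry | Days with a value | Share of full total | Maximum attainable (21 per day; full 315) |
|---|---|---|---|
| Day 13 | 14 | 93% | 294 |
| Day 12 | 13 | 87% | 273 |
| Day 11 | 12 | 80% | 252 |
| Day 10 | 11 | 73% | 231 |
| Day 7 | 8 | 53% | 168 |

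**4. Effect on an arm mean.** Assumptions, not in the documents: true totals of 30 to 45, flat scores, last entry on Day 10, three of 15 subjects in one arm and none in the other.
- Loss per affected subject: 4/15 × 30 = 8, to 4/15 × 45 = 12 points.
- Shift in the arm mean: 3/15 × 8 = 1.6, to 3/15 × 12 = 2.4 points.
- Relative to plan: 1.6/22.21 = 7%, to 2.4/22.21 = 11%.
- If all three are on placebo, normal-approximation power with the SD unchanged falls from 82.0% to 76.1% (1.6 points) or 72.7% (2.4 points). If all three are on OC459, the apparent benefit grows by the same 1.6 to 2.4 points.

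**5. Wider range.** With an assumed 2 to 5 points a day, 3 to 7 days lost and 1 to 3 of 15 placebo subjects affected, the shift runs from 1/15 × 3 × 2 = 0.4 to 3/15 × 7 × 5 = 7.0 points (2 to 32% of 22.21). Power then runs from 81% to 50%.

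**6. If symptoms are falling.** Assume 4 a day on Days 0 to 10 and 1 a day on Days 11 to 14. The true total is 44 + 4 = 48, the partial sum 44 (92%), and the mean recorded score times 15 is 60. Flat scores therefore overstate the loss here, and scaling up the recorded mean overshoots by more than the partial sum falls short.

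**The case against.** Several stronger readings are tempting and do not hold.

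- **Unrecorded days count as zero symptoms.** This is the literal result of totalling every patient and imputing nothing else, but no sentence says it. SAP 7.5 speaks of extrapolation, though it gives no formula for it, and a missing total is equally possible. What stands is that the case is unspecified.
- **The protocol replaces anyone with an incomplete diary.** It replaces those withdrawn, discontinuing or lost to follow-up who fail the criteria. Someone who attends Day 42 with a diary that ended on Day 10 is not clearly any of these.
- **The protocol drops a subject for one missed entry.** The complete diary is given there as a gloss on having enough data, so this is only its strictest reading.
- **Any gap biases the total low.** A diary entry on any of Days 15 to 42 supplies the later value. Only permanent stopping matters.
- **The bias favours the drug.** Only if it falls mainly on OC459; on placebo it hides benefit.
- **One subject's loss of 8 to 12 points is about half the planned difference.** That compares an individual total with a difference in group means.

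It can also be said that the per-protocol analysis is a safeguard, since a subject missing 4 of 15 days (27%) is excluded there and SAP 7.3.1 gives more weight to results on which both sets agree. This is partly right. But a diary ending on Day 12 or 13 is missing only 13% or 7% and stays in both sets. At exactly 3 of 15 days, SAP 7.2 excludes the subject (20% or more missing) while SAP 5.3 keeps them (at least 80% provided).

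**Conclusion.** The point holds in a limited form. The protocol and SAP differ on whether a confirmed-infected subject with an incomplete diary belongs in the primary analysis. For a diary that stops before Day 14 and never resumes, the SAP gives no valid primary total: the result is a partial sum biased low or an unplanned missing value. As nothing has been imputed, the sensitivity analysis is not triggered.

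The likely size is modest: 1.6 to 2.4 points in an arm mean, 7 to 11% of 22.21, for three diaries in 15 ending on Day 10. That rests on assumed totals, flat scores and truncation in one arm only. It would be smaller if symptoms are resolving by Days 11 to 14, which is plausible since SAP 7.4.4 looks for the peak within Days 0 to 10. It would be larger if diaries stop earlier. The documents do not say how often diaries stop, so they do not support a claim that the primary result will be materially biased. They do support settling the rule before the treatment code is broken.

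**What to change.** 1. **One rule** in Protocol 4.4 and 9.17 and SAP 4.7 and 5.2, for both evaluability and replacement. Keep confirmed-infected subjects with partial diaries in the FAS; a minimum number of entries there would add a post-randomisation exclusion. State what shows that 14 days were completed, and define or delete the data condition in SAP 4.7. The same sentences give the replacement target as 20 (protocol) and 30 (SAP); only 30 matches 15 per group, so align these too.
2. **In SAP 7.5**, add wording such as: *Where no diary entry follows (or precedes) a gap, the Day 0 to Day 14 total will not be summed over fewer days. The missing daily scores will be handled under the missing-at-random assumption by [named method], using all recorded daily scores and allowing for change over time.* A repeated-measures model or multiple imputation of the daily scores would serve. Name the covariance structure in advance: an unstructured one over 15 days has 15 × 16/2 = 120 parameters, too many for about 30 subjects. If multiple imputation is used, say how the Mann-Whitney results are combined. Extend the sensitivity analysis to these subjects whether or not anything was imputed.
3. **Collect the Day 0 to Day 14 scores on about Day 14 or 15**, by making one call of the telephone contact already offered in Protocol 9.1 a scheduled one.
4. **Reconcile SAP 5.3 and 7.2** at exactly 3 of 15 days missing.

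The cost is wording in both documents, slightly more analysis work and one scheduled call per subject. The sample size does not change.
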